7. STUDY-WIDE NUMBER OF SUBJECTS*

N/A

8. STUDY-WIDE RECRUITMENT METHODS*

N/A

9. STUDY TIMELINES*

Enrollees in the pre-pilot will participate for 4 weeks. We anticipate this will require 6 months to complete.

Enrollees in the pilot will participate for 8 weeks, in addition to a 3-month follow-up. We anticipate this will take 9-12 months.

The study will require 36 months.

10. STUDY ENDPOINTS*

Outcome Measures:

- The Edinburgh Postnatal Depression Scale (EPDS) is a well validated¹⁰⁸, widely deployed, 10-item scale designed specifically for use with pregnant and postpartum individuals to measure depressive symptoms^{109,110}; a cutoff of 13 is the most specific to identify individuals who likely have an MDE.¹¹¹ This will be used to screen for depressive symptoms and as an outcome measure.
- The CAT-MH including the CAT-DI¹¹² is a computerized adaptive test that draws from an item bank of 452 items; individuals typically need to answer 12 items to render an accurate diagnosis of an MDE. The CAT DI module has a sensitivity of 0.92 and specificity of 0.88 when compared to the Structured Clinical Interview for DSM-IV. The CAT-MH is integrated into CIAS 3.0, allowing for seamless integration with other assessments. This will determine who has depression and needs intervention at the outset of the study (exclusion criteria) and will be used as an outcome measure to determine if the intervention decreased the risk of an MDE or anxiety disorder.
- The General Self Efficacy Scale (GSE scale)⁶⁸ has 10 items scored from 1-4 that measures an individual's belief that she can respond to novel or challenging situations. It takes ~2-4 minutes to complete, has a Chronbach's alpha of 0.82-0.93 and in individuals, is a single factor and correlated highly with self esteem and optimism. This is a target of the intervention that is putatively linked with depression risk. We evaluate whether the TMI changes self-efficacy and hence risk of an MDE.
- The Pearlin Mastery Scale (PMS)¹¹³ has 7 items that are scaled 1-4 (1= strongly disagree to 4= strongly agree) with a range of 7-28, and low scores indicating low mastery (Chronbach's

INVESTIGATOR STUDY PLAN - REQUIRED

alpha=0.78). This is also a target of the intervention and may be associated with lower risk of worsening depression.

- System Usability Scale¹¹⁴ has 10 items and is scored 1-5 (strongly agree to strongly disagree). Scores are summed and multiplied by 2.5. A score of greater than 68 is considered above average. This is a measure of acceptability that bears on ability to implement the system.
- User Engagement Scale – short form¹¹⁵ is a 12 item scale that scores from strongly disagree to strongly agree (1-5). It has 4 subscales with 3 items each. The subscales are Focused Attention; Perceived Usability; Aesthetic Appeal; Endurability. The overall reliability (ω) was 0.88 in formative work; subscales have reliability that is close to this statistic. This is an additional measure of acceptability and hence ability to implement the TMI.

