4. OBJECTIVES*

Aim 1: Draw upon the literature and a User Centered Design approach to collect data from content area experts, caregivers, and individuals with lived experience of perinatal depression, to iteratively develop the Text4Moms tool (tailored text messages, video content, and peer navigator dashboard).

Aim 2: Evaluate preliminary effect direction and magnitude of Text4Moms in a pilot randomized trial (Text4Moms vs educational texts; ratio 2:1) with 30 at-risk pregnant individuals not in an MDE. *Compared to participants randomized to the control condition, those in Text4Moms will:* **H1:** show target engagement through improvement in “self-efficacy” of $\geq d = 0.2$ that can protect against development of an MDE; **H2:** show greater decline in Edinburgh Postnatal Depression Scale (EPDS) scores of $\geq d = 0.2$, and items indicative of RDOC constructs of “loss” and “threat.”¹

Aim 3: Examine implementation outcomes by evaluating the usage, acceptability, and feasibility of Text4Moms and its components: **H3:** Participant ratings will average at least 68 on the System Usability Scale for the Text4Moms system and components. **H4:** >70% of patients will show engagement in Text4Moms by opening $\geq 80\%$ of text messages and clicking on $\geq 30\%$ of links to enhanced content. **H5:** $\geq 30\%$ of mothers will engage with the chat and endorse 4 out of 5 on its utility.

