12. DATA AND SPECIMEN BANKING*

De-identified data will be stored in the National Library of Medicine (NLM) on clinicaltrials.gov. Results information will be submitted and will not include individual patient data. Following completion of the study, all identifiers will be permanently deleted after the final report to the sponsor has been completed

13. Data Analysis and Management*

INVESTIGATOR STUDY PLAN - REQUIRED

Data will be collected by tablet and email links in REDCap. Our statistician at Yale will manage the data. To evaluate acceptability and use characteristics, we will collect descriptive statistics on satisfaction, helpfulness, and ease of use (SUS and UES) for the Text4Moms system and components (including chat), measured at the intervention (week 8). For engagement, data from the Text4Moms system will be reported showing the percentage of individuals who engage with Text4Moms and read at least 80% of texts and the percentage of individuals who engage with the chat. Qualitative responses from participants will offer further insight into these outcomes.

For efficacy outcomes, total scores on EPDS, GSE and PMS¹¹³ (scales) and the onset of an MDE will be reported using means and standard deviations; frequencies and percentages for the EPDS, GSE and PMS scores will be reported as linear variables. Multiple regression will be used to test for differences in the EPDS, and the GSE and PMS scores between treatment groups at week 8, adjusting for baseline scores. Generalized estimating equations will be used to explore if changes in EPDS, GSE and PMS scores varied over time from baseline to week 4 and week 8. We will also examine whether the percentage of individuals who experience an MDE at week 4 and/or week 8 differed between treatment groups using chi-square tests.

We will test for target engagement by measuring changes in the self-efficacy construct (GSE and PMS) between the 2 groups at 4 and 8 weeks. We will do the same for RDOC constructs measured with IDS-SR items. As an exploratory analysis, we will estimate correlations between EPDS scores and the GSE and PMS scores with treatment. We note power is not sufficient to detect mediating effects.

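### The System Usability Scale rule as written runs from 25 to 125, so an all-neutral respondent scores 75 and meets the H3 benchmark of 68

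*Combined protocol and SAP*

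**What the plan says.** The SUS entry appears in Section 10 (Study Endpoints) and again, with the same rule, among the measures in Section 11 (Procedures Involved). It says the scale "has 10 items and is scored 1-5 (strongly agree to strongly disagree"), and then: "Scores are summed and multiplied by 2.5. A score of greater than 68 is considered above average".

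H3, under Aim 3 in Section 4, sets the target: "Participant ratings will average at least 68 on the System Usability Scale for the Text4Moms system and components".

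Section 13 (Data Analysis and Management) promises descriptive statistics on "ease of use (SUS and UES) for the Text4Moms system and components (including chat), measured at the intervention (week 8"). It adds no scoring step.

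Two neighbouring entries in Section 10 are useful for comparison. The Pearlin Mastery Scale is coded "1-4 (1= strongly disagree to 4= strongly agree) with a range of 7-28, and low scores indicating low mastery". The User Engagement Scale "is a 12 item scale that scores from strongly disagree to strongly agree (1-5").

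**The concern.** The SUS entry is a complete-looking instruction: code, sum, multiply. It contains no subtraction, no reversal and no range. Taken at its word, it puts the neutral point of the scale above the benchmark that is meant to show good usability.

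The anchors add a second problem. In the order given, 1 is strong agreement and 5 is strong disagreement, so totals rise with disagreement. Yet a high score is treated as favourable. The User Engagement Scale, listed next, orders its anchors the other way, so the SUS direction cannot be taken from a common convention.

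H3 is a named hypothesis with a numeric threshold, and Section 10 describes the SUS as an acceptability measure relevant to implementation. If the rule is programmed as written, the reported H3 conclusion may be the opposite of what a properly oriented score would show. If it is sorted out only after the data are in, the scoring will have been chosen with the result in view.

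**Working it through.** **Inputs.** Ten items, each coded 1 to 5, summed and multiplied by 2.5 (Sections 10 and 11); benchmark 68 (H3 in Section 4; Section 10 uses the same number). The plan states no SUS range or midpoint, and 68 has no inputs in the documents, so there is no stated SUS figure to reproduce.

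**A check on the convention in the same list.** Pearlin: 7 × 1 = 7 and 7 × 4 = 28. This matches the stated range of 7 to 28, which is therefore a plain raw sum without recoding.

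**The SUS rule as written.** Score = 2.5 × (sum of ten items).

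- All 1: 10 × 1 × 2.5 = 25
- All 3 (neutral): 10 × 3 × 2.5 = 75
- All 5: 10 × 5 × 2.5 = 125
- Sum needed for 68: 68 / 2.5 = 27.2, a mean item of 2.72, which is below the neutral code of 3

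The all-neutral 75 satisfies both forms of the threshold, at least 68 (H3) and greater than 68 (Section 10). None of these results depends on item wording.

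**With items first recoded to 0–4 (assumed intent).**

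- Maximum: 10 × 4 × 2.5 = 100
- All neutral: 10 × 2 × 2.5 = 50, below 68
- 68 needs a mean contribution of 2.72 out of 4, equivalent to 3.72 on a 1–5 coding where higher is favourable

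**What a written score of 68 would mean.** This depends on item wording, which the documents do not give. Let f, from 0 to 4, be a respondent's favourability, the same on every item, and let k be the number of items on which a higher code is favourable. Then

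raw sum = k(1 + f) + (10 − k)(5 − f), and the 0–100 score = 25f.

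| Case | Written score | Consequence |
|---|---|---|
| (a) k = 10 | 0–100 score + 25 | 68 corresponds to (27.2 − 10) × 2.5 = 43; means from 43 to just under 68 pass wrongly |
| (b) k = 0 | 125 − 0–100 score | 68 corresponds to (50 − 27.2) × 2.5 = 57; every pass is a score of 57 or lower, and a true 68 becomes 125 − 68 = 57 and fails |
| (c) k = 5 | raw sum 5(1 + f) + 5(5 − f) = 30, so 75 for every f | uniformly favourable, neutral and uniformly unfavourable respondents all score 75 and pass |

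With the anchors in the order stated, case (b) is what results if all ten items are positively worded.

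**The case against.** The best defence is that this is a shortened description rather than a wrong calculation. The scale is cited to a source (reference 114), and the team may well score it as that source directs. Nothing shows that a program will follow the short text literally. Other entries are just as brief: the General Self Efficacy entry gives item codes without anchors or range, the Edinburgh scale entry gives no item coding, and the User Engagement Scale entry gives no overall scoring rule. The Pearlin entry is therefore the exception, and the 2.5 multiplier itself suggests that the SUS is not a plain raw sum. Above average may also mean above other systems rather than above the scale midpoint. In that case a neutral 75 exceeding 68 is strange only if 68 belongs to a 0–100 scale, which the documents do not say. Finally, H3 is descriptive, no decision rule hangs on it, and the score can be recomputed from item responses if they are kept.

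Several of these points stand. The 0–100 scale is an inference, the direction of the error cannot be known without the item wording, and the consequence is confined to one acceptability benchmark that is reported alongside the User Engagement Scale, usage data and qualitative responses.

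They do not rescue the rule. The other brief entries leave scoring unstated, whereas the SUS entry states a procedure, twice, and that procedure is incomplete. Section 13 does not send the analyst to the cited source. In none of the three wording cases is the written score comparable with a benchmark of 68 on 0–100. That the score can be recomputed later limits the damage but does not replace fixing the rule in advance.

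**Conclusion.** The concern holds. That the written rule gives 25 to 125, places neutral at 75 and reaches 68 at a mean item of 2.72 is certain. That H3 can reverse (75 and met as written, 50 and missed when recoded, for a wholly neutral sample) rests on the assumption that 68 refers to a 0–100 scale. The effect on a real sample depends on item wording: a shift of 25 points, an inversion, or a loss of discrimination.

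This should be corrected but does not threaten the trial. No efficacy analysis, sample size, randomisation or safety provision depends on it.

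**What to change.** In the SUS entries of Sections 10 and 11:

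1. State which response is coded 1 and which is coded 5.
2. Recode every item to 0–4 so that higher means more usable, reversing negatively worded items as confirmed against the form actually used.
3. Sum, multiply by 2.5, and state the 0–100 range.

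In Section 13, refer to this rule and say that H3 (mean of at least 68 at week 8) is judged on that scale. Keep item-level responses so that the score can be verified. Settle the rule before any week-8 data are examined.

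The cost is about two sentences in each of two places, a cross-reference and a short scoring program. There is no new data collection and no design change. H3 may look less favourable than under the written rule (cases (a) and (c)) or more favourable for a genuinely usable system (case (b)).

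A separate scheduling point, which does not affect H3: the assessment table in Section 11 marks the SUS and User Engagement Scale at baseline, before anyone has received a text. The table and the text should be reconciled.

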11. PROCEDURES INVOLVED*

Text4Moms intervention and design. Text4Moms will consist of four primary components.

- **First**, it will include a screening tool that will triage individuals to immediate care (an MDE, depressive symptoms or no-minimal depressive symptoms). We envision that the screener will include questions from the EPDS¹⁰⁸ but will also run a Computerized Adaptive Technology program called CAT-MH.¹¹² This program was integrated into CIAS and by clicking a link, participants can run CAT-MH. The program uses adaptive branching to select questions that determine whether the participant likely is in an MDE episode and thus requires a higher level of care.
- **Second** and most centrally, Text4Moms will include tailored text messages that are readily accessible to participants and, after consent is obtained, will arrive without requiring the participant to seek them out. This novel pro-active approach can enhance engagement among participants.
- **Third**, Text4Moms will include extended content that will be available as a simple link within text messages. We estimate that approximately half of all Text4Moms messages will include a link. Content will be kept extremely brief to increase the likelihood that even modestly motivated participants will click. All extended content will provide information regarding how to find additional information and higher-level support and will come in two forms: a) brief videos, tailored to participant needs and characteristics and designed to be consistent with the ROSE prevention models; and b) interactive micro-interventions approximately 60 seconds in duration, built using CIAS. These micro-interventions can themselves include brief video content or can involve short interactions with an animated narrator in which the participant can securely indicate their feelings or preferences and receive reflections and tailored information in response.
- **Fourth**, Text4Moms will include on-demand live chat access to a trained peer navigator who has access to pre-populated scripts. Available through a text message link or a link within a CIAS micro-intervention, this feature will allow secure (silent and end-to-end encrypted) contact with a peer who can provide social support or assistance with accessing services.

Peer Support. Our training of peers will be assisted by input from our consultants [name] who has conducted many studies in this arena; and [name], Executive Director

INVESTIGATOR STUDY PLAN - REQUIRED

of Postpartum Support International (PSI). We anticipate recruiting qualified peers from PSI and local resources. Peers will also receive training on how to be a peer, the limits of a peer, safety protocols for participants who show clinical worsening, including suicidal or homicidal ideation and use of the CIAS platform, all following adapted versions of existing peer training and supervision materials developed by [name], with ongoing support provided through regular meetings with the project manager (trained and supervised by [name]). Importantly, all chat conversations between peers and participants can be readily reviewed and monitored, facilitating accurate supervision and support. Support materials, protocols, and texts to provide participants will also be available on the CIAS dashboard.

Peers will interact with participants using a dashboard within CIAS allowing them to view multiple chat threads at once message with participants one at a time, and access manualized content/key resources from a library of available messages. Through these four components, the Text4Moms intervention will be high-reach and low-burden, with a very high proportion of participants getting at least some key content. At the same time, the provision of attractive and brief extended content may allow participants with greater needs to receive assistance where and when they want it, ranging from simple information provision to direct interactions with a trained helper.

Aim 1: To iteratively develop the Text4Moms screening form, tailored text messages, video content, peer navigator manual and understand the population for whom it is needed. The development process is outlined in Figure 5. This addresses step 1 in PAR-21-131 in that it will help us understand the target population and ensure that the intervention is appropriate for the patients, providers, and settings relevant to perinatal depression. We will draw upon the literature with regard to behavioral interventions to prevent peripartum depression as well as new material from mHealth interventions for depression that employ text messages. We will collect expert opinion from two groups: 1) a Patient Guide Group (PGG) that consists of a diverse group of individuals with lived experience of perinatal depression, and 2) an Expert Advisory Board (EAB) comprised of team members and consultants with clinical and research experience in perinatal depression prevention and support of peer navigators (Drs. [name], [name], [name], [name] and [name]).

The core research team will develop a moderator guide to query information. This will be vetted with the EAB. The core team will interview individuals with lived experience of depression from the PGG and conduct a needs assessment that provides information directly from individuals including:

- their struggles with depression and areas where they perceive help would have been beneficial
- their course of illness and when help would have been needed and accepted
- barriers to receiving texts, engaging with video links, and using the chat function
- factors to tailor on that would help with engagement
- lessons to amplify with video texts that would make them more useful
- ways peers can be helpful
- areas to avoid if possible
- acceptable quantity (e.g., up to 5 messages per week), frequency (e.g., no more than once a day or every other day), and timing (e.g., between 10AM and 4PM) of text messages

INVESTIGATOR STUDY PLAN - REQUIRED

- ways in which the intervention can fit in with perinatal care

[figure not shown]
The EAB will contribute expertise on:

- important areas of focus
- perceptions of the active ingredients from existing interventions that could be used in texts and amplified in video content. While some are noted above, they will be flushed out during the development process.
- tailoring factors, which are powerful components of engagement. Candidates include: race/ethnicity, age (adolescent up to age 22 vs older mother), marital status, stage of pregnancy, etc.
- areas where video examples are needed to illustrate lessons (e.g., how to interact assertively, to problem solve, to engage others in support)
- materials needed to support peer navigators who communicate with participants over “chat” functionality
- protocols for peers to help manage and refer participants who may evidence clinical deterioration, including suicidal and homicidal ideation
- ways the intervention can fit with perinatal care sites
- how to include perinatal providers.

After individual PGG interviews are completed, the core team will develop a message bank, peer support materials, CIAS micro-interventions, and videos. Additionally, we will search the internet and educational resources for open-source video content. The PI and Co-I [name] will convene the EAB. Using a ‘think-aloud’ approach¹¹⁶, we will ask members to think aloud while reviewing topics, messages, and possible video content. A member of the research team will take notes to capture comments and suggestions. It is likely that additional video content or revisions to available content will be needed. Accordingly, we will encourage ‘virtual white board’ drawings of suggested video content and animations.¹¹⁷ We will draft video content using virtual storyboards, sketches, and accompanying script. After the group has reached 80% consensus on the utility of prototypes, they will be presented to the PGG. We anticipate at least 2-3 meetings of the PGG to review and iteratively improve the materials developed by the research team and EAB. Iterations will include a health literacy evaluation to ensure that audiences who have a low level of literacy will find texts understandable.¹¹⁸ From the PGG, we will elicit feedback on the content modification. [name] team will develop the new multimedia components, if needed. We will also solicit input on the message frequency and timing and peer helpfulness.

INVESTIGATOR STUDY PLAN - REQUIRED

As part of the development process and to test the TMI in the field, we will conduct a pre-pilot study of 10 pregnant individuals, the recommended number of individuals for usability testing.¹¹⁹ We will follow the approach outlined for Aim 2 (see 3.C.4.e) except there will be no

randomization and the intervention timeline will be shortened. The pre-pilot participants will be either before 16 weeks or in the end of their third trimester of pregnancy and will participate for 4 weeks in order to capture various stages of pregnancy and the postpartum period. We will stagger recruitment and have 2 groups of 5 participants. The first group will start the pre-pilot at time T1, and the second group starts at time T1+1 month. This will allow us time to collect feedback after 2 weeks from group 1 and make adjustments (if any) needed to improve the intervention for the second group. The pre-pilot is important since it will allow us to evaluate the usability issues that can come up only after repeated use in the users' native environment, allowing us to address these issues before proceeding to a feasibility pilot. We will also be able to pre-pilot the peer mentor chat support. This step will confirm that all major issues related to use and usability are resolved before going into the pilot, which entails a 2-month intervention and 3 months follow up. Based on the feedback, which will focus on the points covered in PGG meetings, usability of the technology and acceptability of the intervention, we will make a final set of refinements to the multimodal intervention and move to a pilot study.

Aim 2 & 3: Evaluate preliminary efficacy, mechanisms, and implementation of Text4Moms in a pilot randomized trial.

Inclusion/Exclusion Criteria. We realize that the sample size for the pilot is small and will seek to recruit a cohort that is racially, ethnically, and socioeconomically diverse. Individuals will be eligible if they are: a) "at risk" as determined by: an EPDS¹⁰⁸ score of at least 9, or an average score >3 on the 6-item Medical Outcomes Social Support Survey (MOS)¹²⁰, and/or history of an MDE in pregnancy or postpartum depression;^{55,121} b) at least age 16; c) willing and able to provide informed consent. We allow individuals who are as young as 16 because this is a high-risk group for perinatal depression and information on preventative interventions from this group is important. Pregnancy confers "emancipated" status in Massachusetts, so these adolescents will be able to provide consent for participation. Pregnant individuals who are younger than 16 are uncommon in our setting.

Individuals will be excluded if they: a) are in an MDE, have panic disorder or substance use disorder; b) are planning on terminating pregnancy; c) do not want to use a smart phone to receive texts; d) are currently in behavioral health care treatment; e) do not speak English. While

INVESTIGATOR STUDY PLAN - REQUIRED

our software can accommodate other languages, the research team will vet the information sent via chat and it is preferable to do this in English during the intervention development phase. Future work will not include this exclusion and will explore cultural tailoring that goes beyond language.

Recruitment: See #24

Enrollment: The full trial consent will also be presented electronically with study staff on the phone and available to answer questions. Drs. [name], [name] and [name] are currently using this method for consent in their other studies. Participation will proceed only if individuals provide written informed consent via e-signature. This functionality is available in CIAS 3.0. Participants who meet all eligibility criteria and provide consent will then be randomly assigned to either educational texts or Text4Moms after completion of the baseline assessment. We will monitor recruitment for diversity. The staff member who enrolls the participant will not have access to the assigned condition/content, which will aid in blinding study staff.

Clinical Trial Process Procedures

Assessments. After the participant signs consent, we will send her a link to complete a REDCap baseline assessment that includes questions not necessary for eligibility but are important for the study:

- Additional necessary demographic/contact/treatment information
- Additional history of depression/anxiety/psychosis
- Questions that identify domains that the patient identifies as challenging (e.g., low self-esteem, difficulty with role transitions)
- Questionnaires in Table 1

The baseline assessment will be short and will not duplicate information from the screening and eligibility assessment. Individuals will receive a brief reassessment at 4 weeks that includes the EPDS, the CAT-MH, the General Self Efficacy Scale (GSE Scale), the System Usability Scale (SUS)¹¹⁴ and User Engagement Scale (UES)¹¹⁵ that will allow us to collect and address areas related to usability and ensure the intervention content is accessible to all participants. There will be an 8 week assessment that repeats these questions and the CAT-MH. The final assessment will also include the SUS and UES as well as questions on satisfaction of the system, relevance to their issues, what they liked about the system, and what they did not like. Study staff will contact all participants at 3 months to obtain additional qualitative input. The research team will also evaluate the number of individuals who ask to stop texts, number of texts received, and number of links that are opened.

INVESTIGATOR STUDY PLAN - REQUIRED

- Select items from the Inventory of Depressive Symptomatology (QIDS)¹²² that map onto RDOC domains⁵¹ of negative valence (loss and threat) and positive valence (hedonia and reward): impaired capacity for pleasure, impaired general interest, impaired mood response to desired events, impaired energy level for reward and feeling anxious or tense, panic/phobia, interpersonal sensitivity for loss and threat. This will illustrate salience with RDOC constructs that map onto neural pathways that are putatively linked with depression.

MEASURE	Baseline	4 Wks	8 Wks
EPDS	X	X	X
MOS	X		X
QIDS items that track RDOC	X		
CAT-MH	X	X	X
General Self Efficacy	X	X	X
System Usability Scale	X	X	X
User Engagement Scale	X	X	X

- The CAT-MH including the CAT-DI¹¹² is a computerized adaptive test that draws from an item bank of 452 items; individuals typically need to answer 12 items to render an accurate diagnosis of an MDE. The CAT-DI module has a sensitivity of 0.92 and specificity of 0.88 when compared to the Structured Clinical Interview for DSM-IV. The CAT-MH is integrated into CIAS 3.0, allowing for seamless integration with other assessments. This will determine who has depression and needs intervention at the outset of the study (exclusion criteria) and will be used as an outcome measure to determine if the intervention decreased the risk of an MDE or anxiety disorder.
- The General Self Efficacy Scale (GSE scale)⁶⁸ has 10 items scored from 1-4 that measures an individual's belief that she can respond to novel or challenging situations. It takes ~2-4 minutes to complete, has a Chronbach's alpha of 0.82-0.93 and in individuals, is a single factor and correlated highly with self esteem and optimism. This is a target of the intervention that is putatively linked with depression risk. We evaluate whether the TMI changes self-efficacy and hence risk of an MDE.
- The Pearlin Mastery Scale (PMS)¹¹³ has 7 items that are scaled 1-4 (1= strongly disagree to 4= strongly agree) with a range of 7-28, and low scores indicating low mastery (Chronbach's alpha=0.78). This is also a target of the intervention and may be associated with lower risk of worsening depression.
- System Usability Scale¹¹⁴ has 10 items and is scored 1-5 (strongly agree to strongly disagree). Scores are summed and multiplied by 2.5. A score of greater than 68 is considered above average. This is a measure of acceptability that bears on ability to implement the system.
- User Engagement Scale – short form¹¹⁵ is a 12 item scale that scores from strongly disagree to strongly agree (1-5). It has 4 subscales with 3 items each. The subscales are Focused Attention; Perceived Usability; Aesthetic Appeal; Endurability. The overall reliability (ω) was 0.88 in formative work; subscales have reliability that is close to this statistic. This is an additional measure of acceptability and hence ability to implement the TMI.

Study Process: After randomization, participants will be sent texts 3-4 times per week (this may change depending upon input from the PGG). Texts will be short and for the TMI, will include video links that reinforce information relevant to IPT. Texts will also be tailored for stage of pregnancy, history of perinatal depression, and possibly other factors such as age depending upon input from the PGG and the EAB. Texts will continue for 8 weeks unless the participant elects to “STOP” texts. They will include a button that will invite individuals to chat with a peer.

INVESTIGATOR STUDY PLAN - REQUIRED

Control Condition: The control condition will be limited to texts related to pregnancy, nutrition and sleep and will avoid elements that have behavioral therapeutic effects. We will develop a set of texts from openly available information about healthy pregnancy. Although this condition is meant to constitute time and attention control as recommended by an NIH expert panel¹²³, we will include material on recognizing depression and links to ways to attain depression treatment and suicide hotline information.

Peers: We will employ 2-3 individuals as peers; these will be individuals who experienced perinatal depression or were close to someone with perinatal depression. We will recruit from social media, contact providers and the local chapters of PSI. Peers will be encouraged to cluster their texts and will be paid hourly for training and meetings and a modest amount for each text (~\$5). CIAS 3.0 will include a variety of phrases, messages and resources that can be copied and pasted into the chat and thus help peers with messaging about content. Chats will be monitored by the study team. This will ensure the safety of participants and peers and will allow the study team to know if the content is being utilized. Peers will have a safety protocol should a participant experience psychiatric worsening and/or develop suicidal ideation.

Randomization. The 30 participants for the pilot will be randomized in a 2:1 ratio for Text4Moms: Educational control. We acknowledge that the short duration of an R34, and the need to spend at least a year building the system, limits our follow-up period. To collect information about the TMI functionality at various times in pregnancy and after delivery, we will stratify enrollment to 15 individuals who are before 24 completed weeks of pregnancy and 15 who are after 24 completed weeks of pregnancy. This will allow us to pilot the TMI in all phases of pregnancy and the postpartum period since the TMI will endure for 8 weeks. The statistician will generate an allocation sequence for a random-permuted block randomization using identification numbers. After a participant meets criteria and provides consent, the statistician will email the research assistant (RA) the randomization condition. The RA will have no prior knowledge of the randomization sequence. Randomization will occur by the toss of a coin and will not rely on factors other than the stratification.

In year 2, we will recruit 10 individuals who are pregnant for a pre-pilot who will participate for 4 weeks. We will reimburse them \$20 for screening, \$25 at baseline, \$25 at 2 weeks, and \$25 at 4 weeks (Total= \$95 each). Toward the end of Year 2, beginning of Year 3, we will recruit 30 individuals for an 8-week pilot randomized clinical trial with a 3-month follow up. They will be reimbursed \$20 for screening, \$25 at baseline, \$25 at 4 weeks, \$25 at 8 weeks, and \$25 at 3 months (Total= \$120 each). We include \$700 in years 2 and 3 for screening reimbursement. All compensation will be in the form of an Amazon gift card.

